6. STATISTICAL ANALYSIS

6.1. Dataset Generation

Subjects will wear wrist devices with specially configured study software to enable the collection of a single sensor dataset for each subject. The subjects' sensor datasets will be used as the common source of data for this study to which the algorithms will be applied in a *post-hoc* fashion.

For evaluation of the IRNF, the algorithm software will collect accelerometer data continuously and PPG data when the user is still, which is when it would be possible for a tachogram for either the predicate or test algorithms to be collected. The platform and device algorithms for the test and predicate devices will be run on the sensor dataset to generate tachograms and notifications. The performance of the test device will be compared to the performance of the predicate device according to the pre-specified analyses as outlined below.

For the AFBF, the platform algorithm will be applied to reflect the tachogram sampling strategy that will be implemented in the final, finished product. The algorithm parameters associated with minimum requirements to produce the 7-day AF burden measurement will be finalized prior to database lock. The AFBF algorithm will be run on the subjects' sensor datasets to estimate the 7-day average AF burden and identify AF episodes. Additionally, the algorithm will be applied to the set of tachograms generated via the IRNF 2.0 algorithm and compared to the corresponding ECG strips adjudicated by US Board Certified Cardiologists. The AFBF analyses will be performed on all subjects in Cohorts 3 and 4.

6.2. Statistical Methodology

For all of the IRNF statistical analyses, atrial fibrillation (AF) and atrial flutter (AFL) will be treated as a single category of "AF". For all of the AFBF statistical analyses, atrial fibrillation (AF) will be considered its own unique category (i.e., atrial flutter will not be included as part of the detection of AF episodes).

6.2.1. Randomization Methodology

A summary of the randomization methodology applied in this study is outlined below. Additional details may be found in the study Statistical Analysis Plan (SAP).

Wrist Device Assignments

Subjects will be randomly assigned to wear two wrist devices [REDACTED] from the same series/configuration. A pre-determined block randomization schedule will be generated for each enrollment cohort and subjects will be assigned sequentially to either a [REDACTED] [REDACTED]

IRNF

[REDACTED]

To assess overall tachogram performance, a least burdensome approach will also be used

AFBF

6.2.2. Primary Endpoint Analysis

IRNF

Two separate tables will be generated for subject-level data cross-classified by the test device and the predicate device results as presented below for the data collected on all subjects in Cohorts 1 and 3, and 4. One table will be diagnosis of at least one AF episode of at least 30 seconds present on the ECG patch ([Table 5](#)) to assess sensitivity and the other table will be no AF episodes present on ECG patch ([Table 6](#)) to assess specificity per the ECG patch diagnosis definition presented in Section [5.5.2.1](#). AF will be defined as any AF of at least 30 seconds duration by ambulatory ECG patch report. A concordant notification is defined as ≥ 30 seconds of AF present on ECG patch as determined by AF onsets/offsets + cardiac technician overread during the time period defined by the first and last tachograms comprising the alert. A discordant

notification is defined as a notification that is not concordant. Each subject can be represented once and in only one of the cells of the tables below.

Table 5: Diagnosis of ≥ 1 AF Episode Present on ECG Patch

Test Device (IRN 2.0)		Predicate Device (IRN 1.0)		
		≥ 1 Notification		No Notifications
		≥ 1 Concordant	All Discordant	-----
≥ 1 Notification	≥ 1 Concordant	a	b	c
	All Discordant	d	e	f
No Notifications	-----	g	h	i

By defining N1 as the sum of all subjects in [Table 5](#) above, the sensitivity of the test device will be estimated as $(a+b+c)/N1$ and the sensitivity of the predicate device will be estimated as $(a+d+g)/N1$.

Table 6: No AF Episodes Present on ECG Patch

Test Device (IRN 2.0)		Predicate Device (IRN 1.0)		
		≥ 1 Notification		No Notifications
		≥ 1 Concordant	All Discordant	-----
≥ 1 Notification	≥ 1 Concordant	-----	-----	-----
	All Discordant	-----	r	s
No Notifications	-----	-----	t	u

By defining N2 as the sum of all subjects in [Table 6](#) above, the specificity of the test and predicate devices will be estimated as $(t+u)/N2$ and $(s+u)/N2$, respectively.

Usable wrist device data that aligns with and corresponds to the time interval during which the ECG patch is worn will be used for this analysis.

Only subjects in Cohorts 1, 3, and 4 will be included in the primary endpoint analysis.

[REDACTED]

[figure not shown]
[REDACTED]

[REDACTED]

[REDACTED]

AFBF

A single weekly AF burden estimate will be recorded for both the test device and the ambulatory ECG Patch reference method for all subjects contributing usable data in Cohorts 3 and 4. █

The primary endpoint hypothesis associated with the AFBF algorithm is:

The results will also be graphically displayed on a Bland-Altman Plot.

6.2.3. Secondary Endpoint Analyses

IRNF

The notification-level PPV of AF by ambulatory ECG at the time of any tachogram comprising the notification will be estimated for both the test and predicate device algorithms. The notification-level PPV is defined as the proportion of notifications where at least one of the ECG strip results associated with the spot tachograms that comprise the notification exhibits AF of at least 10 seconds per the ECG strip diagnosis definition presented in Section 5.5.2.1.

Notification-Level PPV = (# of notifications with an adjudicated ECG strip diagnosis of AF of at least 10 seconds for any tachogram comprising the notification) / (# of alert notifications)

For subjects who exhibit a high level ($\geq 95\%$) AF burden, it is expected that a large (100 to 200) number of notifications will be generated in total for both the IRN 1.0 and 2.0 algorithms resulting in $>1,000$ tachograms per subject in Cohort 4. For these subjects who are permanently in AF, a least burdensome approach will be followed where for all notifications generated from subjects in Cohorts 1 and 3 and randomly selected notifications from subjects in Cohort 4 will be included in this analysis. A corresponding adjudicated ECG strip diagnosis will be determined for all tachograms comprising these notifications.

Because the set of notifications may differ between the test and predicate device algorithms and because multiple notifications may be associated with some subjects, a bootstrap approach will be implemented to obtain 95% two-sided confidence intervals separately for each algorithm's notification-level PPV. The bootstrap sampling will randomly select subjects who have analyzable data with replacement rather than individual data points to account for any correlation structure that might exist within subjects so that confidence limits are corrected for within-subject correlation.

Two tachogram-level analysis results

associated with the secondary endpoints

of tachogram performance will be reported separately for each device algorithm using tachograms generated by subjects in Cohorts 1, 3, and 4. Separate contingency tables cross-classifying the adjudicated cardiologist diagnoses from ECG strips with the binary classification of tachogram results for test and predicate devices will be presented as outlined in [Table 7](#) below.

Table 7: Cross-Classification Table of Tachogram Results and Adjudicated Cardiologist Diagnoses from ECG Strips

Tachogram Result	Adjudicated Cardiologist Diagnosis					Total
	SR	AF	Atrial Flutter	Other Irregular Rhythm	Uninterpretable	
Irregular	n11	n12	n13	n14	n15	nTI
Not AF	n21	n22	n23	n24	n25	nTN
Total	nSR	nAF	nAFL	nOA	nU	N

Abbreviations: SR = sinus rhythm; AF=atrial fibrillation; AFL=atrial flutter

Tachogram performance for the test and predicate devices will be estimated separately as outlined below because the set of tachograms will differ by device. Two-sided 95% bootstrap confidence intervals will be constructed for each performance metric by randomly selecting subjects who have analyzable data with replacement to account for any within subject correlation of multiple tachograms associated with each subject.

Tachogram Sensitivity = $(n12+n13)/(nAF+nAFL)$

Tachogram Specificity = $n21/nSR$

Tachogram False Positive Rate = $(n11+n14)/(nSR+nOA)$

Tachogram PPV = $(n12+n13)/(nTI-n15)$

Tachogram NPV = $n21/(nTN-n25)$

The ECG strips corresponding to all tachograms which comprise each notification for subjects in Cohorts 1, 3 and 4 from the test and predicate device algorithms will be adjudicated and included in the analysis of this secondary endpoint.

AFBF

A tachogram-level analysis associated with the secondary endpoint of tachogram performance for the AFBF will be reported by cross-classifying the binary classification of tachogram results with the adjudicated cardiologist classifications from ECG strips where the SR and Other Abnormal Rhythm adjudications are combined into a single category. [REDACTED]

Using the notation of [Table 7](#), tachogram performance will be estimated as outlined below from the randomly selected tachograms for all subjects in Cohorts 3 and 4. Two-sided 95% bootstrap confidence intervals will be constructed for each performance metric to account for potential within subject correlation of the multiple tachograms associated with each subject.

- Tachogram Sensitivity = $n12/nAF$
- Tachogram Specificity = $(n21+n23+n24)/(nSR+nAFL+nOA)$
- Tachogram PPV = $n12/(nTI-n15)$
- Tachogram NPV = $(n21+n23+n24)/(nTN-n25)$

Although the set of tachograms for the AFBF device algorithm will differ from the set of tachograms generated from the test IRNF device algorithm, [REDACTED]

[REDACTED] The same tachogram performance analysis of the AFBF device algorithm will be performed as specified above.

The analysis of the day-specific AF burden estimate will be performed to demonstrate that the algorithm provides accurate estimates of AF burden regardless of the set of days included in the analysis using a Monte Carlo simulation based approach. In this approach and at each iteration of the simulation, days will be selected at random (and without replacement) for each subject from the set of days where reference and test device data is available. An AFB measurement will be determined from the test device across the selected days as will the reference AFB measurement for each subject. [REDACTED]

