Total Number of Study Subjects Enrolled	
 A total of n=235 to 627 subjects across the following 4 cohorts are targeted for enrollment in this study as follows: 
 n=78 (Cohort 1: No Known Diagnosis of AF) n=67-85 (Cohort 2: Aggressor Rhythm Cohort) n=54-394 (Cohort 3: Non-permanent cohort, Paroxysmal, Persistent or Chronic AF) n=36-70 (Cohort 4: Permanent AF) 
Additionally, there will be a sub-study of approximately 40 participants prior to the pivotal study starting, which would bring the total sample size to 667. The sub-study participants are a separate cohort and will not be included in any of the endpoint analyses for the pivotal study (see section 3.1 Study Design - Overview).

TABLE OF CONTENTS

SYNOPSIS4

TABLE OF CONTENTS.....	9
LIST OF TABLES.....	11
LIST OF ABBREVIATIONS.....	12
1. INTRODUCTION	14
1.1. Background.....	14
1.2. Device Description	15
1.3. Study Rationale.....	15
1.4. Risk/Benefit Assessment	15
2. STUDY OBJECTIVES, ENDPOINTS, AND HYPOTHESES	16
2.1. Study Objective	16
2.2. Study Endpoints	16
3. STUDY DESIGN	19
3.1. Overview.....	19
3.2. Required Equipment	20
3.2.1. Sponsor-Provided	20
3.2.2. Contract Research Organization (CRO)-Provided	20
3.2.3. Storage and Handling Procedure	20
3.2.4. Accountability.....	20
3.2.5. Investigational Study Site-Provided	20
3.3. Qualification Criteria for US Board-Certified Cardiologists.....	20
3.4. Randomization and Blinding	20
3.5. Duration of Subject Participation	21
4. STUDY POPULATION.....	22
4.1. Subject Recruitment.....	22
4.2. Study Cohorts and Target Population.....	22
4.3. Inclusion Criteria	23
4.4. Exclusion Criteria	24
4.5. Subject Discontinuation.....	25
4.6. Subject Follow-up.....	25
5. STUDY PROCEDURES	26

5.1.	Screening	27
5.2.	Study Day 1	27
5.2.1.	Data Collection Study Equipment Set up	27
5.3.	Study Days 1-13	28
5.4.	Study Day 5	28
5.5.	End of Study Visit	28
5.5.1.1.	Study Procedures	28
5.5.1.2.	Wrist Device Data Processing	29
5.5.2.	Adjudication of ECG Data.....	29
5.5.2.1.	ECG Patch	29
6.	STATISTICAL ANALYSIS	32
6.1.	Dataset Generation.....	32
6.2.	Statistical Methodology	32
6.2.1.	Randomization Methodology	32
6.2.2.	Primary Endpoint Analysis.....	33
6.2.3.	Secondary Endpoint Analyses	36
6.2.4.	Safety Analyses	39
6.2.5.	Additional Analyses.....	39
6.3.	Sample Size Determination	41
6.4.	Significance Level	43
6.5.	Missing Data	44
6.6.	Subgroup Analyses	44
6.7.	Interim Analyses.....	44

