Recent guidelines and professional society consensus documents highlight the importance of enhancing patient knowledge of AF ([January, 2019](#); [Lane, 2015](#)). Given that mobile devices permit ways to frequently monitor patients in an outpatient setting, our hypothesis is that use of the test device can facilitate both the identification of AF in the undiagnosed users as well as provide valuable information regarding AF burden estimates for users with known diagnosis of AF.

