2.2. Study Endpoints

Primary Endpoints:

IRNF:

- Sensitivity of the irregular rhythm notification for the identification of persons with AF by 13-day ambulatory ECG, with AF defined as at least 30 seconds of AF by ambulatory ECG.
- Specificity of the lack of irregular rhythm notification for the identification of persons without AF by 13-day ambulatory ECG, with AF defined as at least 30 seconds of AF by ambulatory ECG.

AFBF:

- Weekly AF burden estimate, defined as the percentage of time a subject is in Atrial Fibrillation during wrist device wear over the prior 7 consecutive days

Secondary Endpoints:

IRNF:

- Notification-level positive predictive value (PPV) with AF by ambulatory ECG at the time of any tachogram comprising the notification.
- Tachogram-level performance (Sensitivity, Specificity, false positive rate (FPR), PPV, negative predictive value (NPV)) for tachograms comprising alerts.
- Tachogram-level performance (Sensitivity, Specificity, FPR, PPV, NPV) for all generated tachograms.

AFBF:

- Sensitivity, specificity, positive predictive value, and negative predictive value of tachograms for the identification of AF by ambulatory ECG.
- Day-specific AF burden estimate defined as the percentage of time a subject is in Atrial Fibrillation during a specific day of the week.
- Four-hour segment-specific AF burden estimate defined as the percentage of time a subject is in Atrial Fibrillation during a specific four-hour segment of a day.

Study Hypotheses

IRNF:

The primary endpoint hypothesis associated with the IRNF is:

[REDACTED]

[REDACTED] Data from subjects in Cohorts 1, 3, and 4 will be used to test this hypothesis.

The secondary endpoint hypothesis associated with the IRNF compares the tachogram-level false positive rate (FPR) of the test device to that of the predicate device to determine if the test device algorithm FPR is non-inferior [REDACTED] to that of the predicate device using all tachograms generated only from subjects in Cohort 2 (Aggressor Rhythm Cohort). [REDACTED]

[REDACTED]

AFBF:

The primary endpoint hypothesis associated with the AFBF is:

[REDACTED]

The secondary endpoint hypotheses associated with the day-specific and four-hour segment-specific endpoints are listed below, respectively:

[REDACTED]

[REDACTED]
[REDACTED]
[REDACTED]
[REDACTED] Additional
information on the simulation methodology is contained in Section 6.2.3 and the SAP.

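### Pooled IRNF PPV reflects a sample recruited largely for known AF and overstates PPV for undiagnosed users, by an amount that depends on accuracy and prevalence the document does not give

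*Combined protocol and SAP*

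**What the plan says.** Section 2.2 lists "Notification-level positive predictive value (PPV) with AF by ambulatory ECG" among the IRNF secondary endpoints. It also lists tachogram-level sensitivity, specificity, FPR, PPV and NPV, once for tachograms that make up alerts and once for all generated tachograms.

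Under Section 6.2.3 the tachogram results are "reported separately for each device algorithm using tachograms generated by subjects in Cohorts 1, 3, and 4". The formulas are raw counts from Table 7: PPV = (n12+n13)/(nTI−n15) and NPV = n21/(nTN−n25). Notification-level PPV uses every notification from Cohorts 1 and 3 and a random selection from Cohort 4; the number selected is not visible. Cohort 2 is in neither analysis.

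The synopsis gives the mix: "n=78 (Cohort 1: No Known Diagnosis of AF"), "n=54-394 (Cohort 3: Non-permanent cohort, Paroxysmal, Persistent or Chronic AF") and "n=36-70 (Cohort 4: Permanent AF"). Section 4.3 requires a known AF diagnosis for Cohorts 3 and 4, and Sections 3.1 and 4.2 keep them open until AF-burden minimums are reached. Section 1.1 hopes that the device can "facilitate both the identification of AF in the undiagnosed users"; its mention of users with known AF concerns burden estimates.

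**The concern.** PPV and NPV depend on how common AF is in the set that is analysed. Here that is fixed by recruitment quotas, by how long Cohort 3 stays open and, for notifications, by how many Cohort 4 notifications are drawn. None of these reflects the people in whom IRNF is meant to find AF.

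Leaving out Cohort 2, which is enrolled because its rhythms can look like AF, also removes a likely source of false positives. The visible text has no prevalence weighting, no PPV or NPV by cohort, and no statement limiting how the values may be read. Subgroup reporting in Section 6.6 covers primary endpoints only. At stake is whether a reported PPV is taken as the chance that a flag in an undiagnosed user is AF.

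**Working it through.** **1. Enrollment mix (synopsis).** The stated total is reproduced: 78+67+54+36 = 235 and 78+85+394+70 = 627. In Cohorts 1, 3 and 4 the share recruited for AF is (54+36)/(78+54+36) = 90/168 = 53.6% at minimum enrollment and (394+70)/(78+394+70) = 464/542 = 85.6% at maximum. These are recruitment labels. Section 6.2.5 moves AF-recruited subjects with 0% adjudicated burden to final Cohort 1, so the share showing AF will be lower. If only 90 of 542 showed AF (assumption), it would be 16.6%.

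**2. Direction, without knowing accuracy.** PPV/(1−PPV) = [p/(1−p)] × Se/(1−Sp). With Se and Sp held equal, the ratio of PPV odds between two populations is the ratio of their prior odds.
- Prior odds in the pool: 90/78 = 1.15 to 464/78 = 5.95.
- Against an assumed 1% prevalence (odds 1/99): PPV odds about 114 to 589 times higher in the pool.
- Against an assumed 5% (odds 1/19): about 22 to 113 times higher.
- If only 90 of 542 show AF (odds 90/452 = 0.199): about 3.8 times at 5% and 20 times at 1%.

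**3. AF share in tachogram units.** Cohort 3 subjects are in AF only part of the time, so subject shares cannot be applied to tachograms. Assume equal tachograms per subject, 98% burden in Cohort 4 and mean burden of 2% to 50% in Cohort 3.
- Lowest: (394×0.02 + 70×0.98)/542 = 14.1%.
- Highest: (394×0.50 + 70×0.98)/542 = 49.0%.

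For undiagnosed users, assuming 1% to 5% have AF at 2% to 20% burden, the share is 0.01×0.02 = 0.02% to 0.05×0.20 = 1%.

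**4. All-tachogram PPV.** PPV = Se·p/[Se·p + FPR·(1−p)], with Se = 0.90 assumed and FPR = 1−Sp:

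| AF share of tachograms | Sp 99% | Sp 99.9% |
|---|---|---|
| 49% | 0.989 | 0.999 |
| 14.1% | 0.937 | 0.993 |
| 5% | 0.826 | 0.979 |
| 2% | 0.647 | 0.948 |
| 1% | 0.476 | 0.901 |
| 0.2% | 0.153 | 0.643 |
| 0.02% | 0.018 | 0.153 |

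For example, at 1% and Sp 99%: 0.009/(0.009+0.0099) = 0.476. At the person level, with Sp 99.9% and pool shares of 53.6% to 85.6%, PPV goes from 0.999–1.000 to 0.948 at 2% prevalence and 0.979 at 5%, a drop of about 5 and 2 points.

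**5. Notification PPV (counts all assumed).** In the pool, take k notifications retained per Cohort 4 subject, half of Cohort 3 giving 5 true notifications each, and a fraction f of Cohort 1 giving 2 false ones each. At minimum enrollment with f = 5%:
- k = 5: (180+135)/(180+135+7.8) = 0.976.
- k = 100: 3735/3742.8 = 0.998, so the sampling choice alone moves the value.

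For undiagnosed users, assume 80% detection, 5 true notifications per detected person and 2 false per false-positive person. Across f of 0.1% to 5% and prevalence of 1% to 5%, PPV runs from 0.04/(0.04+0.099) = 0.29 to 0.2/(0.2+0.0019) = 0.99.

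**6. NPV.** The planned formula has correctly negative other-irregular strips (n24) in the denominator but not in the numerator. Assume 90%/99% accuracy and that 20% of non-AF strips are other irregular rhythm. At a 1% share, planned NPV is 0.784/0.981 = 0.80, against a textbook 0.980/0.981 = 0.999. At a 50% share, planned NPV is 0.396/0.545 = 0.73. NPV does shift the other way, but textbook figures do not describe it.

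**The case against.** - *PPV decides nothing.* The primary IRNF endpoints are sensitivity and specificity, and the stated secondary hypothesis concerns FPR in Cohort 2. No visible test uses PPV or NPV, and nowhere does the document present the pooled PPV as the probability for an undiagnosed user. This stands and keeps the point to reporting and interpretation.
- *Readers can re-project PPV themselves.* Sensitivity, FPR, the Table 7 counts and further conditional probabilities are planned. That is true, but the plan does not take the step, and a reader who used the planned specificity would go wrong: n21/nSR covers sinus rhythm only.
- *Both algorithms share the mix.* This helps a comparison of test with predicate. Each PPV is nevertheless estimated separately, with its own interval, as an absolute value.
- *Weighting may exist out of sight.* Parts of Sections 6.2.1 and 6.2.3 are redacted, and the SAP to which the protocol refers for detail may add weighting. This cannot be excluded, but the visible formulas contain none.

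Two stronger readings are tempting. A reader might infer that PPV will be near 100% by construction; that depends on specificity, and at a 14% tachogram share with 90%/99% accuracy it is 94%. A reader might also infer that notification PPV is greatly overstated. A notification combines several tachograms, so tachogram specificity does not carry over, and the assumed-count range of 0.29 to 0.99 is too wide to show it.

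**Conclusion.** The point holds as a matter of reporting. The visible IRNF PPVs are unweighted and pooled over a sample in which 53.6% to 85.6% of subjects are recruited for known AF. They describe that mix and overstate PPV in undiagnosed users. The direction needs only comparable sensitivity and specificity in the two populations and a lower AF share in undiagnosed users.

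The size rests on accuracy and prevalence that the document does not give. For all tachograms it is large in most of the cases tried: from 94–99% to 48% at a 1% share with 90%/99% accuracy, and lower at smaller shares. It can be small: a few points at person level with 99.9% specificity and prevalence of 2% or more, and possibly small for notifications. The primary tests and their sample sizes are untouched.

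**What to change.** 1. Label the pooled IRNF PPV and NPV as specific to the enriched study sample.
2. For the all-tachogram analysis only, add PPV standardised by Bayes' rule from the estimated tachogram sensitivity and FPR, not the sinus-rhythm-only specificity. Use a stated range of AF tachogram shares for undiagnosed users and the subject-level bootstrap already planned. If NPV is standardised too, define it conventionally, with n24 in the numerator, and say that it differs from the planned NPV.
3. Do not apply this to tachograms comprising alerts, which are conditioned on an alert having occurred.
4. Report notification PPV by enrollment cohort, with Cohort 1 apart from Cohorts 3 and 4. Final cohort will not serve: Section 6.2.5 defines it by adjudicated burden (0% for Cohort 1, at least 95% for Cohort 4), which pushes PPV close to 0 and 100% by definition.
5. State the Cohort 4 notification sampling fraction, or weight by it.

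The cost is one extra table from estimates already planned, with no new data, and a less favourable PPV. The Cohort 1 notification PPV will rest on few notifications and will be imprecise.

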5.5.2.1.1. Rhythm Diagnoses

The diagnosis of the rhythm will fall into one of five categories:

1. Sinus Rhythm
2. Atrial Fibrillation (AF)
3. Atrial Flutter (AFL)
4. Other irregular rhythms (examples include sinus rhythm with frequent PACs, sinus rhythm with frequent PVCs, SVT, VT/VF)
5. Unreadable as defined that a diagnosis cannot be made as the strip is not adequate for reading

The diagnosis will be made via the following logic flow (in sequential order):

1. If the ECG strip contains at least 10 seconds of continuous atrial fibrillation, then it will be classified as “Atrial fibrillation.” Any atrial fibrillation with PACs or PVCs will be classified as “Atrial fibrillation”, with the note of PACs or PVCs be added to the comments section.
2. Otherwise, if 6 or more of the sub-strips cannot be interpreted (e.g. due to noise or artifacts), then the strip will be classified as “Unreadable.”
3. Otherwise, if the ECG strip contains a non-AF arrhythmia, then it will be classified as “Other arrhythmia”. This includes:
 - Supraventricular Tachycardia (includes atrial tachycardia, AVNRT, AVRT)
 - Sinus rhythm with PACs
 - Sinus rhythm with PVCs
 - Sinus rhythm with junctional beats
 - Sinus arrhythmia
 - Ventricular tachycardia (sustained or nonsustained)
 - Heart Block (includes 2nd or 3rd degree HB)
4. Otherwise, the ECG will be classified as “Sinus rhythm”

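### IRNF tachogram specificity leaves out the other-irregular strips that the false positive rate beside it counts as negatives, so the two secondary metrics do not agree

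*Combined protocol and SAP*

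**What the plan says.** Section 6.2.3 gives five IRNF tachogram metrics on the cells of Table 7, for each algorithm separately, in Cohorts 1, 3 and 4. Four of them matter here:

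- Specificity: "Tachogram Specificity = $n21/nSR"
- False positive rate: "Tachogram False Positive Rate = $(n11+n14)/(nSR+nOA", with the bracket closing after nOA
- Positive predictive value: "Tachogram PPV = $(n12+n13)/(nTI-n15", again with the bracket closing there
- Negative predictive value: "Tachogram NPV = $n21/(nTN-n25", likewise

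The fifth, sensitivity, is (n12+n13)/(nAF+nAFL).

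Two other sections fix what the columns mean. Section 6.2 says that for the IRNF "atrial fibrillation (AF) and atrial flutter (AFL) will be treated as a single category", so flutter belongs to the positive class. In section 5.5.2.1.1 the third step of the reading rule is that "if the ECG strip contains a non-AF arrhythmia, then it will be classified as" other arrhythmia. Its list includes sinus rhythm with PACs, PVCs or junctional beats, and sinus arrhythmia. Sinus rhythm is what remains after the earlier steps.

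For the AFBF, section 6.2.3 uses a wider denominator: "Tachogram Specificity = $(n21+n23+n24)/(nSR+nAFL+nOA".

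**The concern.** With AF and flutter as the positive class, a readable strip in the Other Irregular Rhythm column is a negative. The FPR treats it as one and the specificity omits it. Sections 2.2 and 6.2.3 list both as secondary metrics for the same tachograms, and a reader will take one as the complement of the other.

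The omitted strips are also the negatives on which an irregularity detector is most likely to be tested. A change between the predicate and test algorithms that was confined to such strips would leave the specificity figure exactly where it was, while the FPR moved. Two neighbouring numbers would then tell different stories about the same comparison.

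**Working it through.** **Inputs.** The cell notation is that of Table 7, and the formulas are those of section 6.2.3. The documents state no false-call rates and no rhythm mix, so there is no figure of the plan's to reproduce. Every rate below is an assumption.

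**Step 1: algebra.** Let f_SR = n11/nSR, f_OA = n14/nOA and w = nOA/(nSR+nOA).

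- Printed specificity = n21/nSR = 1 − f_SR
- Printed FPR = (n11+n14)/(nSR+nOA) = (1−w)·f_SR + w·f_OA
- Sum = 1 + w(f_OA − f_SR)

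The sum equals 1 only if w = 0 or f_OA = f_SR. On the FPR's own negatives, specificity is (n21+n24)/(nSR+nOA) = 1 − FPR. The printed figure differs from that by w(f_OA − f_SR).

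**Step 2: does one treatment of the column give all five formulas?**

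| Other Irregular Rhythm treated as | Printed formulas that fit | Printed formulas that do not |
|---|---|---|
| Negative | sensitivity, FPR, PPV | specificity, NPV |
| Excluded | sensitivity, specificity | FPR, PPV, NPV |
| Positive | specificity, NPV | sensitivity, FPR, PPV |

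None does. The negative treatment follows from section 6.2 and fits the most formulas.

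**Step 3: example with assumed counts.** Take 800 sinus strips with 1% false calls and 200 other-irregular strips with 15%. Then n11 = 8, n21 = 792, n14 = 30 and n24 = 170.

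- Printed specificity = 792/800 = 99.0%
- Printed FPR = (8+30)/1000 = 3.8%, so the sum is 102.8%
- Specificity on the FPR's negatives = (792+170)/1000 = 96.2%, which is 2.8 points lower

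Add 500 AF strips at an assumed 90% sensitivity, so that n22 = 50. Printed NPV = 792/(792+50+170) = 792/1012 = 78.3%. With n24 counted as correct it is 962/1012 = 95.1%. Under the printed NPV, even an algorithm with no errors would score nSR/(nSR+nOA) = 1 − w.

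**Step 4: range.** Assume f_SR = 0.5%, so printed specificity is 99.5% throughout. The entries are 1 − FPR = 99.5% − w(f_OA − 0.5%).

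| f_OA | w = 10% | w = 20% | w = 40% |
|---|---|---|---|
| 0.5% | 99.5% | 99.5% | 99.5% |
| 5% | 99.05% | 98.6% | 97.7% |
| 10% | 98.55% | 97.6% | 95.7% |
| 20% | 97.55% | 95.6% | 91.7% |

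The sign can reverse. With f_SR = 1% and f_OA = 0.5%, the printed figure is 99.0%, against 99.02% to 99.25% for w between 5% and 50%.

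**The case against.** The best defence is that a sinus-only specificity was intended. The plan lists specificity and FPR separately, and one would be redundant if they were complements. Section 6.2.5 also reports, for each algorithm, the probability of each device result given Other Irregular Rhythm, with bootstrap intervals. That could be read as one rate per reference category. The AFBF formula proves little about the IRNF, because the AFBF text says explicitly that sinus and other rhythms are pooled and the IRNF text does not.

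The point about the AFBF stands. The intended-design reading does not, because a column that was deliberately set aside would also have to leave the FPR, the PPV and the NPV denominator, and it stays in all three. No visible text explains the mixture. Text near Table 7 is blacked out, and the protocol refers to SAP detail that is not visible, so an explanation may exist there.

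It also stands that the information is not hidden. The omitted strips enter the FPR, the PPV, Table 7 and the section 6.2.5 contingency tables by rhythm sub-category. The section 6.2.5 conditional probabilities are worded for the randomly selected tachograms, however, so they may not cover the separate analysis of tachograms that make up alerts.

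A reader might infer that specificity is certain to be overstated. The documents do not support that. Section 6.3 says only that such arrhythmias can look irregular in the way AF does, and it gives no rates. The other category also takes in sinus rhythm with PACs or PVCs, for which no false-call rate is given either.

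**Conclusion.** The formulas are inconsistent as written, and this should be fixed before analysis. The inconsistency is algebraic and needs no assumption. The direction does need one: printed specificity is above 1 − FPR only if other-irregular strips are falsely called more often than sinus strips. That is plausible but unquantified. Under the rates assumed in the table, the gap runs from zero to 7.8 points. That range is illustrative and is not evidence about this trial.

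Three wider readings should be resisted.

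- The primary result is not touched. Subject-level specificity is (t+u)/N2 in section 6.2.2 and does not use these cells.
- The visible Cohort 2 hypothesis concerns the FPR, not specificity. If it uses the section 6.2.3 formula, it already counts these strips.
- Not every irregular strip outside AF is dropped. Flutter has its own column and enters IRNF sensitivity.

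**What to change.** In section 6.2.3 and the matching SAP text:

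1. Define IRNF tachogram specificity as (n21+n24)/(nSR+nOA), which equals 1 − FPR.
2. Define IRNF tachogram NPV as (n21+n24)/(nTN−n25), so that specificity, FPR, PPV and NPV share one negative class. Changing specificity alone would leave n24 correct in one metric and not in the next.
3. If a sinus-only figure is wanted, report n21/nSR separately, labelled as specificity on sinus-rhythm strips.
4. State in one sentence that Other Irregular Rhythm is a negative category for the IRNF tachogram metrics.

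The cost is two formulas and a label. No new data, adjudication or sample size is needed, and the subject-level bootstrap carries over. Reported specificity would probably fall somewhat. NPV cannot fall, because n24 is added to its numerator and its denominator is unchanged.
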